Hypothesis I-a: C-tDCS will be safe in AIS patients receiving EVT with no increased risk of symptomatic intracranial hemorrhage (SICH) within the 24-hour period after EVT. Hypothesis I-b: C-tDCS will not increase the rates of asymptomatic intracranial hemorrhage, early neurological deterioration (NIHSS during the 24-hour period after stimulation), 90-day mortality, and all serious adverse events. Hypothesis I-c: Majority of AIS patients ($\geq 90\%$) will tolerate the C-tDCS by completing at least 75% of the stimulation period with no major stimulation related pain, discomfort and skin changes.

Specific Aim II: To determine the feasibility of delivering C-tDCS as an adjunct and bridge to EVT.

Hypothesis II-a: Adjunctive C-tDCS after endovascular thrombectomy will be started more rapidly after the end of ET procedure over the course of the study and in the last 10 patients, median time from end of ET procedure to C-tDCS initiation will be ≤ 10 minutes. Hypothesis II-b: Bridging C-tDCS prior to endovascular thrombectomy will be started more rapidly over the course of the study and in the last 4 patients, median time from randomization to C-tDCS initiation will be ≤ 10 minutes.

Specific Aim III: To explore the potential imaging and clinical efficacy of tDCS in AIS as an adjunct and bridge to EVT.

1) Early and late penumbral salvage, defined as proportion of penumbral tissue on baseline multimodal MRI that does not proceed to infarct on 2-hour and 24-hour MRI (PWI); 2) Early and late collateral enhancement, evidenced by reduced perfusion lesion volume on 2-hour and 24-hour perfusion-weighted MRI (PWI); 3) Early and late reduction in infarct growth from baseline to 2-hour and 24-hour MRI; 4) Early improvement in neurologic deficit (NIHSS at 24h); 5) Improvement in final 3-month disability and quality of life (modified Rankin scale, AMC Linear Disability Scale, EQ-5D, and Barthel Index)

Impact

This in-hospital safety trial, will identify C-tDCS dose regimens that are feasible, well-tolerated, and preliminarily safe in patients with acute ischemic stroke who undergo ET. Study finding will identify the most promising dose regimens to advance to phase 2b and pivotal phase 3 efficacy trials for three patient populations with pressing need for improved therapies: 1) thrombectomy-eligible patients arriving directly to thrombectomy-capable hospitals who would benefit from post-arrival brain protection; 2) thrombectomy-eligible patients arriving initially

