The study sample size derives from the use of the 3+3, rule-based, modified Fibonacci, dose escalation design, with 3:1 randomization to active treatment vs sham control. There will be 6 dose tiers, reflecting increasing intensity and duration of stimulation (Figure 7). The 3+3 study design (3 patients and 1 sham) with 6 dose tiers yields a sample size of at least 24 and potentially up to 48. The 3+3 design is the classical approach to dose escalation in first-in-human studies.^{47,48} While newer, adaptive designs for dose escalation trials have been developed, they are more complex and have limited advantages when major toxicities are not expected.⁴⁹ Therefore, the rule-based, 3+3 design remains the dominantly employed approach in current dose-escalation studies. We will take every step to avoid missing data by scheduling of the follow-up visits early in visit time windows and readiness to travel to the patient's location to perform needed assessments. Should any missing data occur, primary analyses will be performed using multiple imputation, with sensitivity analyses including complete case and worst possible outcome analyses.⁵⁰

E.2.2. Baseline characteristics

The demographic and baseline clinical characteristics of the study population will be delineated with standard descriptive statistics. Categorical variables describing the clinical history, examination findings, and initial treatment will be summarized by frequencies. Continuous variables such as vital signs, laboratory results, and time variables will be characterized by means, standard deviations, and 95% confidence intervals (CI). Ordinal and non-normally distributed variables (such as the NIHSS) will be characterized by medians and interquartile ranges. Baseline characteristics will be compared between the tDCS stimulation group with sham group to assess covariate balance. Wilcoxon Rank-Sum tests will be used for continuous or ordinal variables; Fisher's exact tests and chi-square tests will be used for grouped or nominal categorical variables.

E.2.3. Safety and Tolerability (Specific Aim 1)

E.2.3.1 Dose Escalation

The study Data and Safety Monitoring Board (DSMB) will meet at the completion of each dose tier, review all safety data, and determine whether the study will proceed to the next dose tier. DSMB deliberations will be

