guided by: 1) a formal stopping/escalation rule, based on the occurrence of the lead safety endpoint, symptomatic intracranial hemorrhage (SICH), and 2) The DSMB members' clinical judgement upon review of all other safety outcomes. The formal dose escalation rule uses SICH frequency to gate the occurrence and pace of escalation through the 6 dose tiers. If no SICH occurs in the 3 active patients at a dose tier, enrollment may escalate to the next dose tier. If one SICH occurs, 3 more active (and 1 more control) patient will be enrolled at that dose tier before escalation. If 2 SICHs occur at a dose tier, further study enrollment is held until detailed review by the DSMB (Fig 6). In addition, whenever the formal SICH criteria for dose escalation has been met, the DSMB will formally meet, review the SICH data and all other safety data, and advice regarding proceeding to the next tier, continuing at the current tier, or placing the study on hold.

E.2.3.2. Primary Safety Endpoint Analysis

For the final statistical analysis of the primary SICH safety endpoint, a chi-square test will be used to detect differences in the rate of SICH between the active treatment and sham patients and higher and lower dose tiers. The treatment will be considered to have exhibited adequate safety in the current trial to proceed to future, larger, pivotal efficacy trials if tDCS results in lower or equivalent rates of SICH compared to sham.

E.2.3.3. Secondary Safety Endpoints Analysis

In secondary safety endpoint analyses, the following will be compared between the active treatment and sham patients, and between higher and lower dose tiers, using chi-squared tests: **1)** Asymptomatic ICH by 24h (intracranial hemorrhage not associated with NIHSS worsening ≥ 4); **2)** Early neurologic deterioration (worsening ≥ 4 on NIHSS during the 24-hour period after stimulation, with or without intracranial hemorrhage); **3)** All-cause mortality at day 90 (mRS); and **4)** All serious adverse events.

E.3.3. Tolerability Endpoint Analysis

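### The final SICH verdict covers undifferentiated tDCS, names no regimen and is not linked to the tier-level hold rule, so data that trigger a hold can still meet the adequate-safety criterion

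*Combined protocol and SAP*

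**What the plan says.** **Final verdict (E.2.3.2, Primary Safety Endpoint Analysis).** SICH rates are compared by chi-square between active and sham patients, and between higher and lower dose tiers. The decision sentence then uses only the first contrast: "The treatment will be considered to have exhibited adequate safety in the current trial to proceed to future, larger, pivotal efficacy trials", on condition that the tDCS SICH rate is lower than or equivalent to the sham rate. No tier or regimen is named, and *equivalent* is not defined.

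**Tier rule (E.2.3.1, Dose Escalation).** A tier whose three active patients are free of SICH allows escalation. A single SICH adds a second cohort of three active patients and one sham at the same tier. For two events the rule reads: "If 2 SICHs occur at a dose tier, further study enrollment is held until detailed review by the DSMB". Neither section says what a hold means for the final verdict.

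**Size and allocation (E.2.1).** Each cohort has three active patients and one sham, under a scheme "with 3:1 randomization to active treatment vs sham control". The tiers number six, in rising order of current and duration, and the stated total is 24 to 48 patients.

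**Purpose (A. Specific Aims, Impact).** "Study finding will identify the most promising dose regimens to advance to phase 2b and pivotal phase 3 efficacy trials".

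**Wider decision (D.6.10.2).** Whether to go to a pivotal trial, run a larger safety trial or stop is to be judged on all the outcome measures together.

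**The concern.** The six tiers differ in current, in number of cycles and in whether a cycle precedes thrombectomy. The Impact section promises to say which of these regimens should advance, but the decision sentence speaks only of tDCS as a whole. With one sham patient per cohort, a comparison pooled over every enrolled tier is the only workable reading, although the plan never uses the word.

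Patients on the lighter regimens then dilute events on the heavier ones. Because E.2.3.2 does not refer to E.2.3.1, a tier that has reached two SICHs leaves no mark on the verdict. At stake is the claim that can be made about the primary safety endpoint of a first-in-human trial. A report could state that the pre-specified criterion was met without saying that the regimen with the events was the one under review.

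**Working it through.** **1. The plan's own figure.** Six tiers of 3 active + 1 sham give 6 × 4 = 24. If every tier is expanded, 6 × (6 + 2) = 48. The stated 24 to 48 is reproduced.

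**2. When the criterion is met on observed rates.** Let *m* be the number of shams enrolled, so 3*m* are active, with *a* active and *s* sham SICHs. The criterion holds when *a*/(3*m*) ≤ *s*/*m*, that is, when *a* ≤ 3*s*. A hold needs *a* ≥ 2 in one tier.
- *s* = 0: any held trial fails.
- *s* = 1, in any tier: the criterion is met with up to 3 active SICHs, including 2 or 3 in a single held tier.

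**3. Examples with no assumed rate.**

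| Active SICHs | Sham | Active rate | Sham rate | Criterion (observed rates) |
|---|---|---|---|---|
| Tiers 1-5 0/15, tier 6 2/3 (held): 2/18 | 1/6 | 11.1% | 16.7% | met |
| Same | 0/6 | 11.1% | 0% | fails |
| Tiers 1-2 0/6, tier 3 2/3 (held): 2/9 | 1/3 | 22.2% | 33.3% | met |

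In the first row Pearson chi-square gives p = 0.72. Within the active arm, tier 6 against tiers 1-5 (2/3 v 0/15) gives Fisher p = 0.020.

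**4. The tier contrast in E.2.3.2.** It has no defined split, and the answer depends on the split. For the first row:
- tiers 4-6 v 1-3: 2/9 v 0/9, chi-square p = 0.13, Fisher 0.47;
- tiers 5-6 v 1-4: 2/6 v 0/12, chi-square p = 0.034, Fisher 0.098.

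Neither result enters the decision sentence.

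**5. How often (assumed rates; the documents give none).** Suppose tier 6 has a 40% SICH risk and all other patients, sham included, 3%, 5% or 10%. The E.2.3.1 rule is applied tier by tier with one sham per three active, ending at the first hold. That ending is a simplification, since the plan holds only until review.

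Chance that a tier is held once reached = P(≥2 of 3) + P(1 of 3) × P(≥1 of the next 3):
- at 40%: 0.352 + 0.432 × 0.784 = 0.691;
- at 3%: 0.0026 + 0.0847 × 0.0873 = 0.0100;
- at 5%: 0.0073 + 0.1354 × 0.1426 = 0.0266;
- at 10%: 0.0280 + 0.2430 × 0.2710 = 0.0939.

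At the 5% background, tier 6 is reached and held in 0.9734⁵ × 0.691 = 60% of trials. The share of trials held at tier 6 that still have *a* ≤ 3*s*:

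| Background rate | Tier 6 at 30% | Tier 6 at 40% | Tier 6 at 50% |
|---|---|---|---|
| 3% | 16% | 16% | 15% |
| 5% | 25% | 23-24% | 22% |
| 10% | 41% | 39% | 37% |

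As a rough check, the chance of at least one SICH among six shams, 1 − (1 − *p*)⁶, is 17%, 26% and 47%. The table is somewhat lower because held trials with more than three active SICHs need a second sham event. The sham rate drives the result; the assumed tier 6 rate matters little.

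**6. Holds with no device effect.** With the same rate in every patient, at least one of six tiers is held with probability 1 − (1 − *h*)⁶, where *h* is the per-tier figure above: 6%, 15% and 45% at 3%, 5% and 10%.

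**7. Per-tier intervals (Clopper-Pearson, 95%).** 0/3: 0-71%. 1/6: 0.4-64%. 2/3: 9-99%.

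**The case against.** The case on the other side has weight.

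- **E.2.3.2 is not the whole decision.** D.6.10.2 rests the step to a pivotal trial on all outcome measures, E.1 gives the DSMB a review after each tier, and the FDA is notified after one SICH. A reader might infer that the plan would send a regimen with a SICH signal to a pivotal trial. The documents do not support that: these safeguards may well prevent it. They do not, however, amend the written criterion or tie it to a regimen.
- **The section already looks at dose.** The higher-versus-lower contrast is there. What stands is narrower: its split is undefined and it does not feed the verdict.
- **A hold is not a finding of harm.** It pauses study enrolment pending review. A reader might infer that a held tier should be barred from any favourable verdict. The documents do not say so, and step 6 shows that holds occur with no device effect. Automatic exclusion would also override the DSMB's review.
- **Nearly every held trial passes?** If *equivalent* meant a non-significant chi-square at 0.05, at least 99% of held trials would pass, including 2/18 v 0/6 (p = 0.39). The plan does not define the word that way. Nor is this caused by pooling: tier 6 alone, 2/3 v 0/1, gives p = 0.25. It reflects small numbers and an undefined term, which is a separate matter.
- **On observed rates a sham SICH is required.** Correct. At the 5% background, about three quarters of the trials held at tier 6 fail the criterion.

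**Conclusion.** Wrong as written, and it should be fixed, although D.6.10.2 keeps it short of a must-fix. Two rules in neighbouring sections bear on the same endpoint and are not reconciled, and the final one cannot say which regimen it clears. The conflict follows from the 3:1 ratio alone and needs one sham SICH. Its frequency, roughly 16%, 23% or 39% of trials held at tier 6, rests on the assumed rates of 40% in tier 6 and 3%, 5% or 10% elsewhere, on exact 3:1 allocation, on reading the criterion as observed rates pooled over enrolled tiers, and on treating a hold as the end of enrolment. The pooling covers all six tiers only if tier 6 is reached.

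**What to change.** Reconcile E.2.3.1 and E.2.3.2 with a few sentences in E.2.3.2:

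1. State that the SICH verdict applies to named regimens, so that it serves the purpose given under Impact.
2. State that the pooled active-versus-sham comparison is supportive, and cannot by itself declare adequately safe a regimen whose tier triggered the two-SICH hold.
3. For such a tier, report the hold and the outcome of the DSMB review next to the verdict. What a hold implies for the regimen is for the sponsor and the DSMB to specify in advance.
4. Add a table of active SICH counts per tier with exact 95% intervals.

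The cost is a few sentences and one small table, with no extra patients or data. The claim becomes narrower and the per-tier intervals will be visibly wide, which is a fair picture of three to six active patients per tier.

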The lead safety endpoint adverse event is symptomatic intracranial hemorrhage (SICH), defined using the SWIFT PRIME trial criteria ⁴⁶: an increase of 4 or more points on the NIHSS within 24 hours of stimulation associated with parenchymal hematoma type 1 (PH1), parenchymal hematoma type 2 (PH2), remote intraparenchymal hemorrhage (RIH), subarachnoid hemorrhage (SAH), or intraventricular hemorrhage (IVH). In addition, all hemorrhages, both symptomatic and asymptomatic, will also be separately classified and analyzed by radiologic subtype, as hemorrhagic infarction type 1 (HI1), hemorrhagic infarction type 2 (HI2), PH1, PH2, RIH, SAH, or IVH.⁴⁶ A central neuroimaging core lab, blinded to treatment assignment, will review all brain scans obtained at 24h and rate presence and type of radiologic hemorrhagic transformation. In addition, in patients who experienced worsening by 4 or more NIHSS points in the first 24 hours, they will review any and all additional brain MRI or CT scans obtained during the 24h time period,

SICH is the primary safety endpoint of the current trial, but trial results will be assessed on a variety of additional safety, feasibility, and tolerability results as well. It is anticipated that, after completion of the current trial, the judgement of whether to proceed directly to a pivotal trial, to proceed to a larger safety and preliminary efficacy trial, or to not proceed with further development, will rest on a considered and informed assessment of all outcome measures. It is important, therefore, to collect data on a wide range of safety endpoints and a wide range of measures of functional outcome, as is planned in this proposal. In making the selection of a primary safety endpoint, an emphasis was placed on ensuring patient safety throughout the course of the trial by choosing an endpoint with uncontested clinical relevance (Symptomatic Intracranial Hemorrhage).

D.6.10.3 Additional Adverse Events with Specific Interrogation

In addition to general screening for all serious adverse events and focused elicitation of symptomatic intracranial hemorrhage events, the following events will be specifically interrogated for and recorded in the case report forms: skin redness, scalp rash, hair loss, seizure, headache, sensitivity to light, new ischemic stroke, deep venous thrombosis, pulmonary embolism, pneumonia, acute MI.

E. Safety Monitoring

E.1. Data and Safety Monitoring Plan

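### E.2.3.2 makes the SICH rate alone sufficient to declare safety adequate for pivotal trials, while D.6.10.2 rests that decision on all outcome measures; the two must be reconciled

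*Combined protocol and SAP*

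**What the plan says.** E.2.3.2 gives the chi-square test for SICH and then the criterion: "The treatment will be considered to have exhibited adequate safety in the current trial to proceed to future, larger, pivotal efficacy trials if tDCS" meets one condition. That condition is that active treatment "results in lower or equivalent rates of SICH compared to sham". It names no other endpoint and refers to no other section.

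E.2.3.3 covers the remaining safety endpoints: "In secondary safety endpoint analyses, the following will be compared between the active treatment and sham patients", and also between higher and lower tiers. The endpoints are asymptomatic intracranial hemorrhage by 24 hours, early neurological deterioration, day-90 mortality and all serious adverse events. It sets no threshold and does not say what the results mean for the adequacy conclusion.

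D.6.10.2 confirms SICH as the primary safety endpoint but adds that "trial results will be assessed on a variety of additional safety, feasibility, and tolerability results as well". It expects that the choice between a pivotal trial, a larger safety trial and no further development "will rest on a considered and informed assessment of all outcome measures".

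Section A, Hypothesis I-b, sits under the safety aim and states that "C-tDCS will not increase the rates of asymptomatic intracranial hemorrhage, early neurological deterioration", 90-day mortality or serious adverse events.

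E.1 and E.2.3.1 have the DSMB review all safety data when each tier is complete and advise on escalating, staying at the tier or holding the study.

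**The concern.** E.2.3.2 is the only place where the plan says what result counts as "adequate safety in the current trial to proceed to future, larger, pivotal efficacy trials". Its *if* makes the SICH comparison sufficient. D.6.10.2 describes the same step as a judgement on everything measured. The two agree only if the E.2.3.2 criterion is necessary but not sufficient, and E.2.3.2 does not say that.

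The gap matters because serious harm can fall outside SICH. SICH needs a worsening of at least 4 NIHSS points within 24 hours together with a listed hemorrhage type. Early deterioration in E.2.3.3 is counted "during the 24-hour period after stimulation, with or without intracranial hemorrhage", so non-hemorrhagic worsening is recorded but does not enter the criterion. The same holds for later deaths that do not follow a SICH. A report that applies E.2.3.2 literally could state that safety was adequate for pivotal testing beside a table showing a marked excess of deaths.

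**Working it through.** **Sample size (E.2.1).** Six tiers of 3 active + 1 sham give 6 × 4 = 24 patients (18 active, 6 sham). If every tier is expanded, 6 × 8 = 48 (36 active, 12 sham). This reproduces the plan's range of 24 to 48.

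**Reading of the rule.** E.2.3.2 gives no margin for equivalence. I read it as met when the observed active SICH rate is no higher than the observed sham rate. The examples below use equal rates, so they do not depend on that choice.

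**Example at 24 patients.** SICH 0/18 v 0/6 meets the rule. Suppose deaths are 9/18 v 0/6.
- Uncorrected chi-square = 24 × (9×6 − 9×0)² / (18×6×9×15) = 24 × 2,916 / 14,580 = 4.8, p = 0.028.
- Fisher exact p = 0.052.
- E.2.3.2 verdict: adequate safety.

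**Example at 48 patients.** Suppose SICH is 0/36 v 0/12 and deaths are 18/36 v 0/12.
- Uncorrected chi-square = 48 × (18×12 − 18×0)² / (36×12×18×30) = 48 × 46,656 / 233,280 = 9.6, p = 0.0019.
- Fisher exact p = 0.0015.
- E.2.3.2 verdict: adequate safety.

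One qualification applies to the second example. Under the escalation rule a tier expands after one active SICH, so 48 patients reached by that rule alone imply at least 6 active events. Zero events at 48 would require the DSMB to have kept tiers open. With SICH 6/36 v 2/12 (16.7% in each arm) the rule is met in the same way, and the deaths still do not count.

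**Would a mechanical gate on the other endpoints help?** Assume 90-day mortality of 15% in both arms (not in the documents). Let a and s be independent binomial death counts in nA active and nS sham patients. The chance that observed mortality is higher on active is the sum of P(a)·P(s) over all pairs with a/nA > s/nS.
- 18/6: 1 − 0.529 = 0.471.
- 36/12: 1 − 0.523 = 0.477.

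A no-excess requirement on mortality alone would therefore fail a treatment with no effect on death almost half the time, and it is one of four endpoints. A significance requirement errs the other way. For assumed mortality of 30% active v 15% sham, the exact power of the uncorrected two-sided 5% chi-square test to show harm is 0.054 at 18/6 and 0.148 at 36/12.

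**The case against.** The best defence is that E.2.3.2 is headed as the primary endpoint analysis and gives only that endpoint's criterion. E.2.3.3 follows directly with the other safety comparisons, D.6.10.2 expressly qualifies the role of SICH, and the DSMB sees all safety data between tiers. Read together, progression is already a judgement on everything.

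Much of this stands. A reader might infer that excess deaths cannot stop the programme. The documents do not support that: D.6.10.2 lets any outcome weigh against a pivotal trial, and the DSMB can advise a hold. A reader might also infer that E.2.3.2 contradicts Hypothesis I-b. It does not, because all four I-b endpoints are tested in E.2.3.3; what is missing is a stated link from those results to the adequacy conclusion.

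Nor should a simulated frequency be taken as the size of the problem. With equal SICH of 2%, 5% or 10% and mortality of 40% v 15% (all assumed), 46–55% of completed trials meet the SICH rule and also show an observed death excess of at least 15 points. Counted over all trials started, the range is 27–54%. Among trials that meet the rule, 73–74% show such an excess, but 17–21% do so even when mortality is 15% in both arms. The simulation also leaves out DSMB judgement, and independence from mortality is built into a SICH-only rule.

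The defence does not remove the textual fault. E.2.3.2 says that safety *will be* considered adequate and that this suffices for pivotal trials, whereas D.6.10.2 is worded as an expectation. The DSMB's stated role concerns moving between tiers, not the final verdict, and no section makes its tier review wait for day-90 outcomes.

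**Conclusion.** The point holds as an inconsistency between E.2.3.2 and D.6.10.2. As written, the E.2.3.2 verdict is sufficient on SICH alone and cannot respond to harm outside the SICH definition, even at 18/36 v 0/12 deaths. This follows from the wording and needs no assumed event rate; the examples show what the rule permits, not how often it would happen. It is limited to the formal adequacy statement, since other parts of the plan can still stop progression. The advice against an automatic gate rests on the assumed mortality rates and on the 6 to 12 sham patients that the design provides.

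**What to change.** In E.2.3.2, change *if* to *only if* and state that the SICH criterion is necessary but not sufficient. Add that the adequacy conclusion is made under D.6.10.2 after a documented review of the E.2.3.3 endpoints (asymptomatic intracranial hemorrhage, early deterioration, 90-day mortality, serious adverse events), each shown as an active-minus-sham difference with an exact 95% confidence interval. Cross-refer the two sections. Do not add an automatic no-excess or significance condition.

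The cost is a few sentences and a set of tables from data already collected. The downside is that the verdict becomes less automatic and slightly harder to reach.

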The lead tolerability endpoint is completion of the protocol-assigned stimulation treatment without early cessation due to cutaneous, neurologic, nociceptive or other adverse effects. Experience with tDCS in post-stroke patients indicates only infrequent cutaneous (itching, tingling) adverse effects are likely to occur. Accordingly, for the current study, a patient will be considered to have tolerated the procedure if at least 75% of the stimulus period was completed. The treatment will be considered generally tolerable if, among all enrolled patients, tolerated procedures are achieved in $\geq 90\%$ of patients, assessed with a one-sided p value of 0.025. Secondary tolerability endpoints will be the rate and severity of cutaneous, neurological, and pain items of the technician-filled (Figure 7), descriptively compared between active treatment and sham patients, and between higher and lower dose tiers.

E.3.4. Feasibility Endpoint Analysis (Specific Aim 2)

A time-motion analysis and mock run-throughs will be conducted prior to first enrollment. Nonetheless, it is anticipated that processes to optimize rapid placement of the cap and electrodes will continue to improve with experience gained from initially enrolled patients. The predefined success threshold for feasibility will be median times from randomization to bridging C-tDCS initiation and the time from end of EVT procedure to adjunctive C-tDCS initiation ≤ 10 minutes in the last 4 and 10 enrolled patients, respectively.

E.3.5. Exploratory Efficacy Endpoints Analysis (Specific Aim 3)

E.3.5.1. Exploratory Clinical Efficacy Endpoints

This study is underpowered to definitively determine efficacy, so all clinical efficacy analyses will be purely exploratory and descriptive. Four clinical outcome measures were selected based on their reliability, familiarity to the neurologic community, and adaptability for use in patients who have had a stroke. These endpoints are: the modified Rankin Scale (mRS), a rating of global disability; the Barthel Index (BI), a measure of instrumental activities of daily living; the National Institutes of Health Stroke Scale (NIHSS), a measure of neurologic deficit severity; and the EuroQol (EQ-5D), an assessment of health-related quality of life; and AMC Linear Disability Scale, a granular degree of disability.

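### The primary SICH criterion does not define 'equivalent' and gives no margin or significance level, and 6 to 12 sham patients cannot support it on either reading

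*Combined protocol and SAP*

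**What the plan says.** Hypothesis I-a (A. Specific Aims) expects C-tDCS to be safe "with no increased risk of symptomatic intracranial hemorrhage (SICH) within the 24-hour period after EVT". For the final analysis, E.2.3.2 says that "a chi-square test will be used to detect differences in the rate of SICH between the active treatment and sham patients". The same test is also applied across dose levels. The section then treats safety as adequate for larger pivotal trials "if tDCS results in lower or equivalent rates of SICH compared to sham".

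The sample size comes from the 3+3 rule, not from this comparison: E.2.1 says the design "yields a sample size of at least 24 and potentially up to 48", at 3:1. Under E.2.3.1, no SICH in three active patients allows escalation, and one SICH adds three active patients and one sham. Then: "If 2 SICHs occur at a dose tier, further study enrollment is held until detailed review by the DSMB".

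Three other places bear on the point. The tolerability criterion in E.3.3 does have a level, "assessed with a one-sided p value of 0.025". E.2.3.3 compares the secondary safety endpoints between arms "and between higher and lower dose tiers, using chi-squared tests". D.6.10.2 says the judgement on further development "will rest on a considered and informed assessment of all outcome measures".

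**The concern.** A test for a difference cannot by itself show that two rates are equivalent, and E.2.3.2 does not link its test to its criterion. Two readings are natural: (a) the observed active rate is no higher than the observed sham rate; (b) the chi-square test does not show a significantly higher active rate. If they give different answers on the same data, the primary safety conclusion of a first-in-human acute stroke trial depends on a choice that could be made after unblinding.

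The sham arm is also very small and events are likely to be few. The plan labels efficacy in these same patients underpowered and purely descriptive (E.3.5.1), but draws a comparative conclusion for safety.

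**Working it through.** **Inputs.** From the documents: six tiers, 3:1 allocation, and the E.2.3.1 rule triggered by SICHs in active patients (the caption of Figure 7 says this for the one-SICH step). Assumed: SICH rates of 1% to 10%, a two-sided 0.05 level, and a hold treated as a stop. *Completed* means that all six tiers are cleared without a hold.

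**Sample size reproduced.** 6 × (3+1) = 24 and 6 × (6+2) = 48, as stated. That gives 18 to 36 active and 6 to 12 sham patients.

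**Possible completed trials.** A cleared tier ends at 0/3 or 1/6 active SICHs. With k expanded tiers (k = 0 to 6), there are k SICHs in 18+3k active patients and b SICHs in 6+k sham patients.

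**Reading (a).** The trial fails if k/(18+3k) > b/(6+k), that is, if b < k/3. For k = 1, 2 or 3, any trial with no sham SICH fails.

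Worked example at p = 5% in both arms:
- P(0/3) = 0.95³ = 0.8574. P(1/6) = 3 × 0.05 × 0.95² × 0.95³ = 0.1161. The sum is 0.9734.
- P(complete) = 0.9734⁶ = 0.851. Given completion, a tier was expanded with probability 0.1161/0.9734 = 0.1192.
- The fail probability sums P(k) × P(b < k/3):

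| k | P(k given completion) | P(b < k/3) | product |
|---|---|---|---|
| 1 | 0.3792 | 0.95⁷ = 0.6983 | 0.2648 |
| 2 | 0.1283 | 0.95⁸ = 0.6634 | 0.0851 |
| 3 | 0.0232 | 0.95⁹ = 0.6302 | 0.0146 |
| 4 to 6 | 0.0025 | about 0.91 | 0.0023 |

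The total is 0.367.

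The same sum at other equal rates, and with held trials included at the point where they stop:

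| true rate, both arms | fail, completed | fail, all paths |
|---|---|---|
| 1% | 14.9% | 15% |
| 2% | 24.7% | 27% |
| 3% | 31.0% | 34% |
| 5% | 36.7% | 43% |
| 10% | 33.4% | 49% |

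Among the rates tried, the highest figure for completed trials is 37.3%, at 6%.

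**Reading (b).** The case most adverse to active is no sham SICH. Uncorrected Pearson chi-square (two-sided Fisher in brackets):
- 1/21 vs 0/7: p = 0.56 (1.00).
- 6/36 vs 0/12, the worst completed result: p = 0.13 (0.31).
- 9/36 vs 0/12: p = 0.055 (0.088).
- 10/36 vs 0/12: p = 0.040 (0.048). Ten active SICHs cannot occur in a trial completed without a hold.

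So reading (b) fails no completed trial whatever the true rates, and the readings disagree in the 15% to 37% above. Among trials that stop at a hold, only 3/3 vs 0/1 reaches p < 0.05 (chi-square 0.046, Fisher 0.25). More events could accumulate if the DSMB lifts a hold.

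**With a true excess.** At 10% active vs 5% sham, reading (a) passes 50% of completed trials. At 15% vs 5%, 71% of trials are held and 77% of all paths fail reading (a), but 44% of the 29% that complete still pass. That is 13% of trials completing and passing, against 54% at 5% vs 5%. Discrimination is poor, not absent.

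**Validity of chi-square.** Sham is one quarter of the patients, so its expected SICH count is one quarter of all SICHs: below 1 with fewer than four SICHs. The most possible in a completed trial is 6 active + 12 sham = 18, giving 18/4 = 4.5, still below 5. At 5% in both arms, 34% of completed trials have no SICH at all (the statistic is undefined) and 98% have fewer than four; at 10% the figures are 14% and 88%. For E.2.3.3, with 6 to 9 sham patients the expected sham counts with and without the event sum to less than 10, so one is always below 5, however common the event.

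**Precision.** With zero events the exact two-sided 95% upper bound is 1 − 0.025^(1/n): 45.9% for 0/6, 26.5% for 0/12, 18.5% for 0/18 and 9.7% for 0/36.

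**Scale.** At a 5% rate in both arms, an assumed 10-point non-inferiority margin, one-sided 0.025 and 80% power, the sham arm needs (1.960 + 0.842)² × 0.05 × 0.95 × (1 + 1/3) / 0.10² ≈ 50 patients, with 150 active.

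**The case against.** The strongest reply is that E.2.3.2 never says a non-significant test means equivalence. On its plain sense the criterion compares observed rates, and the 15% to 37% is then only a false-fail rate, which is a cautious error for a safety criterion. Patients are protected by a numerical SICH rule at each tier and by DSMB review, and D.6.10.2 rests further development on all outcomes. The percentages also depend on assumed rates, on excluding held trials, and on counting only active SICHs, although the two-SICH step names no arm.

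Part of this stands. The documents themselves show an undefined word and an unlinked test; the percentages illustrate the consequence under assumptions. E.2.3.2 is not the sole basis for proceeding, and tier-level protection is not in question.

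The rest does not remove the problem. Reading (a) is not simply cautious: it fails on a single active SICH and still passes half of completed trials when the active risk is doubled. The sentence before the criterion names a significance test, so reading (b) cannot be ruled out, and E.2.3.2 does not refer to D.6.10.2. Other counting rules do not help: including held trials gives 15% to 49%, and letting sham SICHs trigger the tier rule also gives 15% to 49%. That reading (b) can never fail a completed trial needs no assumed SICH rate, only the 0.05 level.

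**Conclusion.** The concern holds and should be fixed. As written, the same completed trial can be reported as adequately safe or not. With equal true risk the two readings disagree in 15% to 37% of completed trials, assuming SICH rates of 1% to 10%, two-sided 0.05, active-only triggering and a hold treated as a stop. Reading (b) cannot fail a completed trial, reading (a) discriminates poorly, and neither can establish the absence of increased risk in Hypothesis I-a. The conclusion concerns the final comparative statement only, not the escalation rule or DSMB oversight.

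**What to change.** - In E.2.3.2, remove the comparison with sham as the pass/fail criterion, and drop any claim of equivalence or absence of increased risk, there and in Hypothesis I-a.
- Report SICH in each arm with exact 95% confidence intervals, and the active-minus-sham risk difference with an exact 95% interval and Fisher's exact test, labelled descriptive. Treat the higher versus lower tier comparison in the same way.
- Report the escalation outcome by tier alongside, as description and not as a substitute pass rule.
- Refer the decision to proceed to the overall assessment in D.6.10.2.
- Use Fisher's exact test in E.2.3.3 as well; E.2.2 already names it for baseline variables.

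The cost is wording in E.2.3.2, E.2.3.3 and Hypothesis I-a, and a more modest safety claim. No extra patients or data are needed.
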